#### Objectives

**PRIMARY OBJECTIVE:** To determine the safety of AA-ORS among children with mild to moderate stunting, administered as a daily dose over 2 weeks, ad libitum up to 237 ml in 3 hours.

*Safety assessment in children will compare adverse event (AE) and serious adverse event (SAE) rates and changes to dietary and digestive habits between children receiving AA-ORS versus an inactive placebo solution containing no amino acids.*

**PRIMARY OBJECTIVE:** To determine the feasibility and well-tolerated dose of AA-ORS among children with mild to moderate growth stunting administered as a daily dose over 2 weeks, ad libitum up to 237 ml in 3 hours.

*User preferences among children include average daily volume consumed over 14 days, trends in volume consumed, and factors that influence children's willingness and ability to ingest the product as intended.*

**SECONDARY OBJECTIVE:** To determine the perceptions among caregivers on the use and acceptability of this product as a potential intervention for EED.

*Acceptability by caregivers includes factors that influence their willingness to have the product used by their children and their perception of their child's response to its consumption.*

**EXPLORATORY OBJECTIVE:** To determine the impact of AA-ORS on gut dysfunction, metabolism, gut and systemic inflammation, and micronutrient status.

*Impact of AA-ORS on gut dysfunction, systemic inflammation, and micronutrient status will be assessed by comparing non-invasive biomarker levels in blood samples collected following the intervention. These biomarkers will be assessed in both groups at baseline in order to have setting-specific descriptive data with which to power a future EED efficacy trial.*

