#### Endpoints

**Primary:** Adverse events and serious adverse events through 21 days of follow-up, and changes to dietary and digestive habits through day 14 of follow-up.

**Primary:** Average product volume consumed daily through 14 days of follow-up, time trends in average daily volume consumed, and factors that influence children’s willingness and ability to ingest the product as intended.

**Secondary:** Key factors that influence caregiver willingness to have the product used by their children, and their perception of their child’s response to its consumption.

**Exploratory:** Average plasma/serum concentrations of metabolic, gut dysfunction, systemic inflammation, and micronutrient biomarkers at baseline and day 15 of follow-up.

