The study will be double-blinded as both study staff and participants will be blinded to study product allocation. Active and control product bottles will be labeled with identical product information. Each bottle will be also labeled with a randomization number assigned to a particular participant according to the appropriate allocation arm. The randomization list where randomization number and allocation code are provided will be maintained in a secure place by an independent statistician. The participants

will thus be blinded to whether they receive AA-ORS or the control solution. Study staff administering the study product and laboratory staff performing any laboratory testing will also be blinded to the product allocation.

This study will provide critical information about the safety of AA-ORS in this at-risk pediatric population and qualitative and quantitative information on the user-preferred product volume for this age group, palatability, and ease of administration. The study will also describe whether the product can be feasibly consumed for a 2-week period and if there are differences in gut health between AA-ORS and placebo groups based upon diarrhea frequency and plasma biomarkers of systemic inflammation and gut damage/repair at the end of follow-up. However, the study has not been statistically powered or designed to answer such gut health questions. Even though such exploratory comparisons will be underpowered, the baseline and follow-up biomarker data will be useful for informing study design and sample size of future EED clinical trials in this setting.

The questionnaire guides are a mix of structured and semi-structured questions. Structured questions are necessary to standardize responses to questions such as the experience with diarrheal disease treatment. Semi-structured questions allow for flexibility and richness in responses, especially those on perceptions and experiences around AA-ORS use and acceptability. Semi-structured questions are open-ended and allow for probing a participant's answers for in-depth responses. The DO checklist includes a list of questions to assess the administration of AA-ORS and explore ease of use, palatability, and acceptance of the product by the user(s).

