5. Interim visits: RAs will visit the home on days 2, 4, 7, and 14 to collect unconsumed solution, review instructions, provide additional bottles (on days 2 and 7 only), and weigh the children (on days 7 and 14 only).
6. Adverse event check-ins: Periodically during dosing (days 4, 7, 14, and 21), and one week after the end of dosing (day 21), a study nurse will contact the caregiver by phone and check in with the caregiver to assess any potential AE or SAE, complete the routine interval medical history (with feeding and breastfeeding assessment)/stool frequency questionnaire, answer any medical questions, and provide advice, as necessary.
7. On the fifteenth day of follow-up (or within 2 days after), following the 2-week dosing period, patients and their caregivers will return to the clinic for medical evaluation, collection of blood samples, and caregiver IDIs. Samples will be processed and stored for laboratory analyses following the same procedures from the enrollment blood collection.

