#### *Blood Specimen Collection and Processing*

Between 1 and 1.5 ml venous blood will be collected from each child twice—at enrollment and at the post-dosing visit, 15 days after onset of the intervention. A trained phlebotomist will perform venipuncture using a technique appropriate for children who are younger than 2 years old, and a small drop of blood will be blotted from the insertion site and dried on filter paper. Blood samples will be centrifuged into plasma and/or serum within 30 minutes of collection and stored in cryo tubes at less than  $-20^{\circ}\text{C}$  until they can be analyzed. Commercial enzyme-linked immunosorbent assays (ELISA) and a Quansys Biosciences Q-Plex™ panel will be used to quantify plasma/serum micronutrients, EED markers (intestinal fatty acid-binding protein [I-FABP], soluble CD14 [sCD14], glucagon-like peptide 2 [GLP-2], insulin-like growth factor 1 [IGF-1], and fibroblast growth factor 21 [FGF21]), and systemic inflammation (alpha-1-acid glycoprotein [AGP] and C-reactive protein [CRP]). Mass-spectroscopy will be used to evaluate metabolic markers from dried bloodspot (e.g., acylcarnitine profile) to ascertain whether there is a tendency for child metabolism to switch to an oxidative state when supplementing a subset of essential amino acids. Detail provided in Table 5, below.

**Table 5.** Plasma/serum biomarkers assessed in SAFE at enrollment and post-dosing visit.

Biomarker	Assay name	Company	μl of plasma required (per well)
I-FABP	Human I-FABP ELISA	Hycult	25
GLP-2	GLP-2 ELISA Kit	ALPCO	25
IGF-1	Human IGF-I Quantikine ELISA Kit	R&D Systems	20
sCD14	Human CD14 Quantikine ELISA Kit	R&D Systems	10
FGF21	Human FGF-21 Quantikine ELISA Kit	R&D Systems	50
AGP	Q-Plex™ Human Micronutrient (7-Plex)	Quansys	10
CRP			
Ferritin			
sTfR			
RBP4			
Thyroglobulin			
HRP2			
Acylcarnitine	Acylcarnitine profile analysis	Mass spectrometry	40 (80 μl whole blood)
Total			320

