### *Sampling Strategy*

Estimated sample size: We expect to enroll 132 participants, which includes 66 caregivers, and 66 children (aged 12–24 months); half of these child-caregiver pairs will be randomized to receive AA-ORS (n= 33) and half to receive placebo solution (n= 33). We anticipate that there will be a dropout rate not to exceed 10%. We have incorporated this expected withdrawal rate into the final sample size numbers.

For the primary endpoint of safety in this study, 30 subjects in each arm would result in more than 95% probability of observing at least one AE if the rate of that type of event in the subject population after being exposed to AA-ORS is 10%. To have a 95% probability of being able to detect at least one AE if the rate of that event is truly 5%, the sample size would have to be at least 60 per arm. For more

rare events, the sample size would have to be much larger. Table 6 below shows the probabilities of observing an event with various sample sizes and varying true rates of that event in the population.

**Table 6.** Probability (P) of observing none, one, or more adverse events (AEs) at different true rates of AEs in the population.

N (per arm)	Rate of AE	P of 0 AEs	P of 1+ AEs	P of 2+ AEs	P of 3+ AEs
20	0.15	3.9%	96.1%	82.4%	59.5%
	0.2	1.2%	98.8%	93.1%	79.4%
30	0.1	4.2%	95.8%	81.6%	58.9%
	0.15	0.8%	99.2%	95.2%	84.9%
40	0.1	1.5%	98.5%	92.0%	77.7%
	0.15	0.2%	99.9%	98.8%	95.1%
50	0.1	0.5%	99.5%	96.6%	88.8%
	0.15	0.03%	99.97%	99.7%	98.6%
60	0.05	4.6%	95.4%	80.8%	58.3%
	0.1	0.2%	99.8%	98.6%	94.7%

Gray highlighted cells are those with a probability of 95% or higher. Blue highlighted cells are those representing a true AE rate of 0.1 or lower.

Increasing the per-arm sample size above 30 (but < 60) does not add much in terms of increasing the probability of detecting an AE with a true rate in the population of 10%. However, 30 subjects per arm has relatively low power for an efficacy endpoint using biomarkers. For example, a sample size of 30 per arm provides approximately 80% power for a t test to detect a 376 ng/ml (21.9% reduction) difference in soluble CD14 (marker of bacterial translocation) between the arms assuming the mean sCD14 is 1,715 ng/ml in the placebo group. These calculations used data from an infant cohort in Zimbabwe (23) (SD = 520 ng/ml).

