**STUDY ENDPOINTS TO BE ANALYZED AND ANALYTICAL METHODOLOGY**

**Primary:** AEs and SAEs through 21 days of follow-up, and changes to dietary and digestive habits through day 14 of follow-up.

*For AEs and SAEs that occur within 21 days of enrollment, statistical comparisons will be made between the AA-ORS and the placebo solution groups using Fisher's exact test. Changes to feeding habits (normal, less frequent/less volume, more frequent/more volume), diarrhea (1–2, 3–4, 5–7, or 7+ events in 24 hours), and vomiting (none, 1, 2–5, > 6 events in 24 hours, or hospitalization) will be made using chi-square tests.*

**Primary:** Average daily product volume consumed through 14 days of follow-up, time trends in daily volume consumed, and factors that influence children's willingness and ability to ingest the product as intended.

*The average daily volume (and statistical distribution) of solution consumed by children over the 2-week period will be calculated. These descriptive data will be pooled from AA-ORS and placebo arms as the solutions are designed to taste the same. Lowess curves will be used to describe trends in volumes consumed, and linear mixed effects models will be used to test for an association between day of follow-up and product volume consumed. We will use linear regression to identify factors (e.g., child weight, length, and age) associated with a child's average daily intake.*

**Secondary:** Key factors that influence caregivers' willingness to have the product used by their children, and their perception of their children's response to its consumption.

*These qualitative analyses will use ATLAS.ti software to identify and group key themes and topics from IDI notes.*

**Exploratory:** Average plasma/serum concentrations of metabolic, gut dysfunction, systemic inflammation, and micronutrient biomarkers at baseline and day 15 of follow-up.

*Metabolic, EED, systemic inflammation, and micronutrient marker data collected at baseline will be pooled across intervention groups and used to generate descriptive statistics for the study population. The same descriptive statistics will be generated for day 15 of follow-up. Paired student's t test will be used to compare these continuous parameters between baseline and day 15 of follow-up.*

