*Unpaired student's t test will be used to compare these continuous parameters between the two study groups at day 22. A difference with  $P < 0.05$  will be considered statistically significant. However, there is limited statistical power to make such comparisons between study groups for biomarker outcomes.*

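### The only between-arm biomarker test is set at day 22, when no blood is drawn, and it ignores the baseline sample planned for every child

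*Combined protocol and SAP*

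**What the plan says.** All references are to the combined protocol and SAP.

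- **Between-arm test** (C.xi, Study endpoints to be analyzed and analytical methodology, Exploratory): an unpaired t test is to "compare these continuous parameters between the two study groups at day 22", with P < 0.05 as the criterion. No covariate is named.
- **Within-child test** (same paragraph): a paired t test is to "compare these continuous parameters between baseline and day 15 of follow-up". Baseline values are otherwise used only for descriptive statistics pooled over the arms.
- **Blood sampling** (C.iii, Blood Specimen Collection and Processing): each child is bled twice, "at enrollment and at the post-dosing visit, 15 days after onset of the intervention". Key Activities gives the window for the second visit: "On the fifteenth day of follow-up (or within 2 days after), following the 2-week dosing period". Table 4 marks blood draws at enrollment and day 15 only and has no day-22 column.
- **Endpoint** (C.ii, Endpoints): concentrations of metabolic, gut, inflammation and "micronutrient biomarkers at baseline and day 15 of follow-up".
- **Objective** (C.ii, Objectives): the impact of AA-ORS is to be judged by "comparing non-invasive biomarker levels in blood samples collected following the intervention".
- **Power** (C.iii, Sampling Strategy): "a sample size of 30 per arm provides approximately 80% power for a t test to detect a 376 ng/ml" difference in sCD14, with a placebo mean of 1,715 ng/ml and an SD of 520 ng/ml. Study Approach and Study Population adds that "the study has not been statistically powered or designed to answer such gut health questions".

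**The concern.** There are two faults in one sentence of the analysis plan.

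First, the time point does not exist. The last study contact is a phone call on day 21 (up to 3 days later) to close out adverse events, and no blood is taken then. The exploratory objective rests on the post-intervention comparison of the arms, and this is the only test that makes it. The paired test cannot stand in for it. The plan does not say whether that test is pooled or run by arm, and on either reading it contains no contrast between AA-ORS and placebo.

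Second, the test discards information already collected. Baseline blood is drawn from every child, and a child who cannot give a sample is excluded. In a randomized comparison of about 30 per arm, adjusting for baseline usually narrows the interval and removes the effect of chance imbalance at entry. The plan admits that this comparison is short of power, so leaving the baseline out makes a known weakness worse than it need be.

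At stake are the precision and clarity of the exploratory biomarker result, and its use in designing the later efficacy trial.

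**Working it through.** **1. Time point**

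| Place | Time of follow-up biomarker sample or test |
|---|---|
| Study Overview and C.ii, Endpoints | Day 15 |
| C.iii, Key Activities | Day 15, or within 2 days after (day 17 at latest) |
| C.iii, Post-dosing visit | Within 3 days of the final dose (day 17 if the last dose is on day 14) |
| C.iii, Table 4 | Day 15 |
| C.iii, Blood Specimen Collection | 15 days after onset |
| C.xi, paired test | Day 15 |
| C.xi, unpaired between-arm test | **Day 22** |

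Only the last row differs, and no sample supports it.

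**2. The plan's own power figure**

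Inputs from Sampling Strategy: n = 30 per arm, difference 376 ng/ml, SD 520 ng/ml, placebo mean 1,715 ng/ml. The 0.05 level is from C.xi. Sidedness is not stated, so two-sided is assumed.

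- 376 / 1,715 = 21.9%, as stated.
- Standard error of the difference: 520 × √(2/30) = 134.3 ng/ml.
- Standardized difference: 376 / 134.3 = 2.80.
- Normal approximation: Φ(2.80 − 1.96) = 80.0%. Exact noncentral t with 58 df: 78.6%.

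Both agree with the stated figure of approximately 80%. One-sided versions give 87.6% (normal) and 86.9% (t) and do not. The plan's figure is therefore two-sided and unadjusted.

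**3. The same comparison adjusted for baseline**

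With baseline as covariate, the residual SD is 520 × √(1 − r²), where r is the correlation between the baseline and day-15 values. The t distribution has 2 × 30 − 3 = 57 df. The documents do not give r, so a range is shown.

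| Analysis | Residual SD (ng/ml) | Power at 376 ng/ml | Difference detectable at 80% power (ng/ml) | 95% CI half-width (ng/ml) |
|---|---|---|---|---|
| Unadjusted t test | 520 | 78.6% | 382.5 | 268.8 |
| ANCOVA, r = 0 | 520 | 78.6% | 382.6 | 268.9 |
| ANCOVA, r = 0.3 | 496 | 82.3% | 365.0 | 256.5 |
| ANCOVA, r = 0.5 | 450 | 88.9% | 331.4 | 232.8 |
| ANCOVA, r = 0.7 | 371 | 97.1% | 273.3 | 192.0 |

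Half-width is t(0.975) × residual SD × √(2/30). The unadjusted row, for example, is 2.002 × 134.3 = 268.8.

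This formula charges one degree of freedom for the covariate but not the small average variance inflation from chance imbalance, 1/(60 − 4) = 1.8%. Multiplying the variance by 1 + 1/56 gives powers of 77.9%, 81.6%, 88.3% and 96.9% at r = 0, 0.3, 0.5 and 0.7. The picture does not change.

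**4. Why not a change score**

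The SD of change is 520 × √(2(1 − r)). At r = 0.5 this is 520, so a t test on change has the same 78.6% power as the unadjusted test. At r = 0.3 its power is only 64.3%. ANCOVA carries no such penalty at low r.

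**5. Chance imbalance**

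If the baseline SD is also 520 ng/ml, the standard error of the baseline difference between arms is again 134 ng/ml. An imbalance of that size moves the unadjusted day-15 difference by r × 134, or 0.5 × 134 = 67 ng/ml at r = 0.5. That is 67 / 376 = 18% of the difference used in the power statement.

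**The case against.** The strongest reply has four parts.

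- **Day 22 is a slip.** There is only one follow-up sample, so an analyst has only one data set to test and no result would change. That is largely fair. The error is nevertheless certain, it sits in the only between-arm biomarker test, and the time point should be settled in writing before unblinding.
- **Day 22 may come from a longer schedule.** Interim visits tells caregivers to continue doses for the next 20 days, and Safety Monitoring numbers the bottles 1 to 21, against 14 days of dosing elsewhere. This origin is an inference. The conflict over dosing length is a separate matter that the sponsor must reconcile, and correcting the analysis sentence does not resolve it.
- **The t test is valid, and its low power is disclosed.** Both are true. Disclosure does not supply data at day 22, and admitted low power is a reason to use the baseline sample.
- **The size of the gain is assumed.** This stands. At r = 0.3 the gain is under 4 points. sCD14 is one marker among many in Table 5, and the figures are on the raw scale because the documents give no log-scale SD. They also use 0.05 without the Benjamini-Hochberg adjustment that the plan applies to related hypotheses, so absolute power would be lower if the markers form one family.

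The pooled reading of the paired test is the natural one, and the correlation can be derived from the planned data. Those two items are missing detail and carry little weight.

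**Conclusion.** The concern holds. The day-22 time point contradicts every other statement of when blood is taken, and it leaves the test without data as written. Omitting baseline does not invalidate the test but costs precision. For sCD14 at 30 per arm, adjustment would raise power from 78.6% to between 82% and 97%, and lower the detectable difference from 383 ng/ml to between 365 and 273 ng/ml, for assumed correlations of 0.3 to 0.7. With no correlation there is nothing to gain and almost nothing to lose. These sizes rest on the plan's SD, a two-sided 0.05 level and the assumed correlation, and they do not carry over to the other markers. The consequence is confined to the exploratory objective; the safety and volume endpoints and the sample size are untouched. The change should be made before unblinding.

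**What to change.** In C.xi, Exploratory:

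1. Replace day 22 with the post-dosing sample (day 15, with the visit window stated).
2. Replace the unpaired t test with ANCOVA of the day-15 value on arm and baseline value, log-transformed where the marker is skewed. Report the adjusted difference, or ratio on the log scale, with a 95% CI for each marker.
3. Say whether the paired test is pooled or by arm, label it descriptive, and report change by arm.
4. List the baseline and day-15 SDs and their correlation as outputs for planning the future trial.

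The cost is analysis-plan wording. Both samples are already scheduled, and no visit, assay or sample size changes. Separately, the sponsor should reconcile the passages that imply different lengths of dosing.

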#### ISSUES WITH MISSING DATA AND MULTIPLICITY

We will analyze whether there is differential missingness or loss to follow-up by supplementation arm for the primary endpoints. No imputation of missing outcome data is planned. We will adjust the significance level for multiple comparisons by using the Benjamini-Hochberg method to control for the false discovery rate for related hypotheses.

#### *Quality Assurance*

The study will be conducted in full compliance with the protocol and ICH GCP to provide public assurance that the rights, safety, and well-being of trial participants are protected and that the clinical trial data are credible. To ensure quality and standardization, the site will develop standard operating procedures (SOPs) for key protocol procedures and conduct the study guided by the study *Manual of Procedures* or other written guidelines. The site will also develop routine operational checks to verify that critical protocol requirements and procedures are executed correctly and completely at the time the work is being performed. Prior to the initiation of the study, the sponsor will conduct training on the protocol, including applicable SOPs, for study staff.

Clinical and laboratory data for each participant will be abstracted from study CRFs into standardized project files. These data will be entered directly into computers at a centralized site. Information will be cross-checked for accuracy on a biweekly basis. All data, both hard- and soft-copy formats, will be stored in locked cabinets initially at CGH and will be transported to the PATH office in Kisumu after data entry with limited access by project staff only.

Participants will be identified using a unique Patient Identification Number (PID). The code linking the PID to individual identifying information will be kept in a separate secure location by the project coordinator. Clinical staff at CGH will not be able to access identifying information linked to the PID, except to match laboratory results reported by the lab to individual patients.

